5. STUDY DOCUMENTATION

- Study documents must be filled out completely and correctly. Ditto marks are not allowed.
- If an entry has been documented in error put a single line through the entry and initial and date the change. The RPCI Network Monitor must be able to read what has been deleted.
- Do **NOT** use white-out, magic marker, scratch-outs.
- Do **NOT** erase entries.
- Use only black ink for documentation on the accountability form and any other study forms.
- It is the responsibility of RPCI to inform the Investigator/ institution as to when these documents no longer need to be retained. If, for any reason, the Investigator desires to no longer maintain the study records, they may be transferred to another institution, another investigator, or to RPCI upon written agreement between the Investigator and RPCI.

6. **DRUG ACCOUNTABILITY**

Drug accountability must be strictly maintained.

- Responsibility rests solely with the Investigator but can be delegated as appropriate (e.g., to pharmacy personnel).
- A drug accountability record form (DARF) will record quantities of study drug received, dispensed to participants and wasted, lot number, date dispensed, participant ID number and initials, quantity returned, balance remaining, manufacturer, expiration date, and the initials of the person dispensing the medication.
- Study drug supply will only be used in accordance with the IRB approved study.
- Drug accountability forms are protocol and agent specific, they are study source documents and will be used to verify compliance with the study.
- An inventory count must be performed with each transaction. Any discrepancies shall be documented and explained.
- Drug accountability forms must be stored with study related documents.
- Each medication provided for this study and each dosage form and strength must have its own DARF.
- Dispensing the wrong study supply is considered a **medication error**.
- **NEVER** replace investigational agents with commercial product.
- Do **NOT** “transfer”, “borrow” or “replace” supplies between studies.

7. **SERIOUS ADVERSE EVENT REPORTING**

The site Investigator or designated research personnel will report all SAEs, whether related or unrelated to the investigational agent(s) to the **IRB in accordance with their local institutional guidelines**. The site will notify the RPCI Network Monitor within 1 business day of being made aware of the SAE. A preliminary written report must follow within 1 business day of the first notification using the following forms:

- RPCI SAE Source form
- MedWatch 3500A
- See section 10.4 for additional reporting information

A complete follow-up report must be sent to the RPCI Network Monitor when new information becomes available.

8. **UNANTICIPATED PROBLEM REPORTING**

An unanticipated problem (UP) is any incident, experience, or outcome that meets all of the criteria in **Section 10.7**.

For all adverse events occurring that are unanticipated and related or possibly related to the research drug, biologic or intervention, the participating physician or delegated research staff

from each site will notify their local **IRB in accordance with their local institutional guidelines**. The site must also notify the RPCI Network Monitor within 1 business day of being made aware of the Unanticipated Problem by completing the **RPCI Unanticipated Problem Report Form** and faxing or emailing it to the RPCI Network Monitor.

Appendix B ECOG Performance Status Scores

Description	Status
Fully active, able to carry on all pre-disease performance without restriction.	0
Restricted in physically strenuous activity but ambulatory and able to carry out work of a light or sedentary nature, e.g., light housework, office work.	1
Ambulatory and capable of all self-care but unable to carry out any work activities.	2
Capable of only limited self-care, confined to bed or chair more than 50% of waking hours.	3
Completely disabled. Cannot carry on any self-care. Totally confined to bed or chair.	4
Dead	5

Appendix C Calculation for Creatinine Clearance

Cockcroft-Gault Equation*

$$\text{Men: CrCl} = [(140 - \text{YR}) \times \text{ABW}] / (\text{SCr} \times 72)$$

$$\text{Women: CrCl} = 0.85 \times [(140 - \text{YR}) \times \text{ABW}] / (\text{SCr} \times 72)$$

Where:

CrCl is creatine clearance (mL/min)

ABW is Actual body weight (kg)

SCr is serum creatinine (mg/dL)

YR is age (years)

Appendix D Adaptation of the Immune-Related Response Criteria: irRECIST

The following is taken from Bohnsack et al, 2014, 1070P-Adaptation of the Immune Related Response Criteria: irRECIST, Ann Oncol, 25 (suppl 4): iv369 doi:10.1093/annonc/mdu342.23⁽²⁵⁾.

1. Baseline

A. Measurable Lesion Definitions and Target Lesion Selection

- Follow the definitions from RECIST 1.1
- Measurable lesions must be accurately measured in at least one dimension with a minimum size of:
 - 10 mm in the longest diameter by CT or MRI scan (or no less than double the slice thickness) for non- nodal lesions and ≥ 15 mm in short axis for nodal lesions
 - 10 mm caliper measurement by clinical exam
 - 20 mm by chest X-ray

B. Non-measurable Lesion Definitions

- Follow the definitions from RECIST 1.1
- Non-target lesions will include
 - Measurable lesions not selected as target lesions
 - All sites of non-measurable disease, such as neoplastic masses that are too small to measure because their longest uninterrupted diameter is < 10 mm (or < 2 times the axial slice thickness), i.e., the longest perpendicular diameter is ≥ 10 and < 15 mm.
 - Other types of lesions that are confidently felt to represent neoplastic tissue, but are difficult to measure in a reproducible manner. These include bone metastases, leptomeningeal metastases, malignant ascites, pleural or pericardial effusions, ascites, inflammatory breast disease, lymphangitis cutis/pulmonis, cystic lesions, ill-defined abdominal masses, skin lesions, etc.

C. Target and Non-target Lymph Node Lesion Definitions

- Follow the definitions from RECIST 1.1

D. Non-target Lesion Selection

- All lesions or sites of disease not recorded as target lesions should be recorded as non-target lesions at baseline. There is no limit to the number of non-target lesions that can be recorded at baseline.

E. Bone Lesions

- Follow the definitions from RECIST 1.1
- Regardless of the imaging modality blastic bone lesions will not be selected as target lesions. Lytic or mixed lytic-blastic lesions with a measurable soft tissue component ≥ 10 mm can be selected as target lesions.

F. Brain Lesions

- Brain Lesions detected on brain scans can be considered as both target or non-target lesions.

G. Cystic and Necrotic Lesions as Target Lesions

- Lesions that are partially cystic or necrotic can be selected as target lesions.
- The longest diameter of such a lesion will be added to the Total Measured Tumor Burden (TMTB) of all target lesions at baseline.
- If other lesions with a non-liquid/non-necrotic component are present, those should be preferred.

H. Lesions with Prior Local Treatment

- During target lesion selection the radiologist will consider information on the anatomical sites of previous intervention (e.g. previous irradiation, RF-ablation, TACE, surgery, etc.).
- Lesions undergoing prior intervention will not be selected as target lesions unless there has been a demonstration of progress in the lesion.

I. No Disease at Baseline

- If a patient has no measurable and no non-measurable disease at baseline the radiologist will assign 'No Disease' (irND) as the overall tumor assessment for any available follow-up time-points unless new measurable lesions are identified and contribute to the TMTB.

2. Follow-Up

A. Recording of Target and New Measurable Lesion Measurements

- The longest diameters of non-nodal target and new non-nodal measurable lesions, and short axes of nodal target and new nodal measurable lesions will be recorded. Together they determine the Total Measured Tumor Burden (TMTB) at follow-up.

B. Definition of New Measurable Lesions

- In order to be selected as new measurable lesions (≤ 2 lesions per organ, ≤ 5 lesions total, per time-point), new lesions must meet criteria as defined for baseline target lesion selection and meet the same minimum size requirements of 10 mm in long diameter and minimum 15 mm in short axis for new measurable lymph nodes. New measurable lesions shall be prioritized according to size, and the largest lesions shall be selected as new measured lesions.

C. Non-target Lesion Assessment

- The RECIST 1.1 definitions for the assessment of non-target lesions apply.
- The response of non-target lesions primarily contributes to the overall response assessments of irCR and irNon-CR/Non-PD (irNN).
- Non-target lesions do not affect irPR and irSD assessments.
- Only a massive and unequivocal worsening of non-target lesions alone, even without progress in the TMTB is indicative of irPD.

D. New Non-Measurable Lesions Definition and Assessment

- All new lesions not selected as new measurable lesions are considered new non-measurable lesions and are followed qualitatively.
- Only a massive and unequivocal progression of new non-measurable lesions leads to an overall assessment of irPD for the time-point.
- Persisting new non-measurable lesions prevent irCR.

3. irRECIST Overall Tumor Assessments

- **irCR**: complete disappearance of all measurable and non-measurable lesions. Lymph nodes must decrease to < 10 mm in short axis. Confirmation of response is not mandatory.

- **irPR**: decrease of $\geq 30\%$ in TMTB relative to baseline, non-target lesions are irNN, and no unequivocal progression of new non-measurable lesions.
- **irSD**: failure to meet criteria for irCR or irPR in the absence of irPD.
- **irNN**: no target disease was identified at baseline and at follow-up the patient fails to meet criteria for irCR or irPD.
- **irPD**: minimum 20% increase and minimum 5 mm absolute increase in TMTB compared to nadir, or irPD for non-target or new non-measurable lesions. Confirmation of progression is recommended minimum 4 weeks after the first irPD assessment.
- **irNE**: used in exceptional cases where insufficient data exists.
- **irND**: in adjuvant setting when no disease is detected.

For additional information, refer to the following article and online supplemental information:

(26)

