5 PARTICIPANT SELECTION

5.1 Inclusion Criteria

To be included in this study, participants must meet the following criteria:

1. Have a pathologically confirmed diagnosis of colorectal cancer, which is metastatic or otherwise unresectable.
2. Have received at least 1 prior systemic therapy in the metastatic or unresectable disease setting. Patients who have recurred within six months of adjuvant chemotherapy are not required to have received an additional line of chemotherapy.

3. RAS wild-type. Both KRAS and NRAS testing are necessary. The presence of pathogenic mutations in KRAS or NRAS is exclusionary. Primary tumor or metastatic tumor may be tested.
4. Appropriate for anti-EGFR therapy: Naive to anti-EGFR therapy (cetuximab or panitumumab) or a candidate for rechallenge by virtue of the following:
 - a. the investigator deems anti-EGFR retreatment with cetuximab to be a reasonable standard of care option AND
 - b. outcome of prior anti-EGFR therapy was not rapid progression (i.e. ≤ 3 months on therapy) AND
 - c. prior anti-EGFR therapy was administered > 6 months prior to the start of protocol therapy
5. Age ≥ 18 years of age.
6. Have an ECOG Performance Status ≤ 2 . Refer to Appendix B.
7. Have measurable disease per RECIST 1.1 criteria present.
8. Be willing to provide tissue from a newly obtained core or excisional biopsy of a tumor lesion. Newly-obtained is defined as a specimen obtained up to 30 days prior to initiation of treatment on Day 1.
9. Have the following clinical laboratory values (all screening labs must be performed within 14 days of treatment initiation):
 - Hemoglobin ≥ 8 g/ dL
 - Absolute neutrophil count $\geq 1000/ \text{mm}^3$
 - Platelet count $\geq 100,000/ \text{mm}^3$
 - Serum creatinine clearance ≥ 15 mL/min (refer to Appendix C: Cockcroft-Gault Equation).
 - Serum total bilirubin ≤ 1.5 ULN or, direct bilirubin \leq ULN for participants with total bilirubin levels > 1.5 ULN.
 - AST (SGOT) and ALT (SGPT) ≤ 2.5 ULN or, ≤ 5 ULN for participants with liver metastases.
10. Female participants of childbearing potential are to have a negative serum pregnancy test.

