9.3 Non-Target Lesions

All other small lesions (longest diameter < 10 mm or lymph nodes \geq 10 mm to < 15 mm short axis) and non-measurable lesions (i.e., leptomeningeal disease, ascites, pleural or pericardial effusion, inflammatory breast disease, lymphangitic involvement of skin or lung, blastic bone lesions, or abdominal masses / abdominal organomegaly identified by physical exam that is not measurable by imaging) should be identified as non-target lesions and indicated as present in the source documents at baseline. The general location will also be documented on the images drawing a regularly-shaped Region of Interest. Measurements of the non-target lesions will not be performed, but the presence or absence of each should be noted throughout follow-up and evaluation.

- **Complete Response:** Disappearance of all non-target lesions and normalization of tumor marker level, if applicable. All lymph nodes must be non-pathological in size (< 10 mm short axis).
- **Non-Complete Response/Non-Progressive Disease:** Persistence of 1 or more non-target lesion(s) and/or maintenance of tumor marker level above the upper limits of normal.
- **Progressive Disease:** Appearance of 1 or more new lesions or the unequivocal progression of existing non-target lesions. Although a clear progression of non-target lesions is exceptional, in such circumstances, the opinion of the treating physician should prevail and the progression status should be confirmed at a later time.

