9.4 Evaluation of Response

Time point response assessments will be performed every 9 weeks. To determine time point response, refer to **Table 6** and **Table 7** below.

Table 6 Time Point Response Criteria: target (+/- non-target disease)

Target Lesions	Non-Target Lesions	New Lesions	Overall Response
CR	CR	No	CR
CR	Non-CR/Non-PD	No	PR
CR	Not evaluated	No	PR
PR	Non-PD or not all evaluated	No	PR
SD	Non-PD or not all evaluated	No	SD
Not all evaluated	Non-PD	No	NE
PD	Any	Yes or No	PD
Any	PD	Yes or No	PD
Any	Any	Yes	PD

Table 7 Time Point Response Criteria: non-target disease only

Non-Target Lesions	New Lesions	Overall Response
CR	No	CR
Non-CR/non-PD	No	Non-CR/non-PD ¹
Not all evaluated	No	NE
Unequivocal PD	Yes or No	PD
Any	Yes	PD

¹ Non-CR/non-PD is preferred over SD for non-target disease since SD is used as endpoint for assessment of efficacy in trials so to assign this category when no lesions can be measured is not advised.

The best overall response is the best response recorded from the start of study treatment until disease progression/recurrence or study discontinuation, taking into account any requirement for confirmation. In general, the participant's best response assignment will depend on the achievement of both measurement and confirmation criteria and will be determined by combining the participant's status of target lesions, non-target lesions, and new lesions.

- Symptomatic Deterioration: Participants with global deterioration of health status requiring discontinuation of treatment without objective evidence of disease progression at that time, and not related to study treatment or other medical conditions should be reported as progressive disease due to "symptomatic deterioration." Every effort should be made to document objective progression even after discontinuation of treatment due to symptomatic deterioration. Symptomatic deterioration that may lead to discontinuation of treatment include, but is not limited to, symptoms such as:
 - Weight loss > 10% of body weight.
 - Worsening of disease-related symptoms (e.g., worsening dyspnea, increasing pain/increasing requirement for narcotic analgesics).
 - Decline in performance status of > 1 level on ECOG scale.

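### Appendix D contradicts itself on irPR, so a partial responder whose non-target lesions have all resolved can be scored irSD

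*Combined protocol and SAP*

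**What the plan says.** Objective response by irRECIST is a secondary objective and endpoint (Sections 3.2 and 4.1.1). Section 12.3 says that it will be tabulated and that secondary analyses are descriptive. The operative definitions are in Appendix D.

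- Appendix D, Section 3, sets three conditions for irPR: a fall of at least 30% in total measured tumor burden (TMTB) from baseline, then "non-target lesions are irNN, and no unequivocal progression of new non-measurable lesions".
- The same list defines irNN as an overall assessment: "no target disease was identified at baseline and at follow-up the patient fails to meet criteria for irCR or irPD".
- The same list makes irSD the default for anyone who meets neither irCR nor irPR and does not have irPD.
- Appendix D, Section 2.C, says "Non-target lesions do not affect irPR and irSD assessments". It spells irNN out as irNon-CR/Non-PD, and adds "The RECIST 1.1 definitions for the assessment of non-target lesions apply".
- Section 9.3 defines the lesion-level non-CR/non-PD state as "Persistence of 1 or more non-target lesion(s) and/or maintenance of tumor marker level above the upper limits of normal".
- Table 6 in Section 9.4 gives an overall PR when target lesions are in PR, there are no new lesions, and non-target lesions are "Non-PD or not all evaluated".
- Inclusion criterion 7 in Section 5.1 reads "Have measurable disease per RECIST 1.1 criteria present".

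**The concern.** There are two problems. First, Section 2.C removes non-target status from the irPR decision and Section 3 puts it back as a condition. Both cannot govern. Second, the condition uses a label with two meanings, and neither meaning covers a patient whose non-target disease has cleared completely.

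The irSD default turns this into a scoring error rather than a gap: a patient who misses irPR on wording is not left unclassified but counted as a non-responder. The Section 3 wording also reverses the natural order, because complete clearance of non-target disease scores worse than persistence of it. Two assessors who both follow Appendix D could code the same scan differently, and the tabulated rate would depend on which rule each had in mind.

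**Working it through.** The plan gives no figure for irRECIST response, so there is none to reproduce. The check applies each rule to three follow-up records. In all three, TMTB is down 45% from baseline (an example value beyond the 30% threshold), some target disease remains, and there are no new lesions. The table shows the time-point assessment, before any confirmation requirement.

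| Non-target status | Section 3, irNN as the overall category | Section 3, irNN as non-CR/non-PD | Section 2.C | Section 9 (Tables and definitions) |
|---|---|---|---|---|
| A. Lesions persist, not progressing | irSD | irPR | irPR | PR |
| B. All lesions resolved (non-target CR) | irSD | irSD | irPR | PR |
| C. None at baseline | irSD | unclear | irPR | PR |

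Reasoning by record:

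1. None of the three is irCR, because that needs all measurable and non-measurable disease to disappear. None is irPD. Each is therefore irPR or, by default, irSD.
2. Record A is irPR once irNN is read as the lesion-level state in Section 9.3, since persistence of a non-target lesion is exactly that state.
3. Record B does not meet that state: nothing persists. It fails the second irPR condition and falls to irSD. Section 2.C ignores non-target status and gives irPR. In Table 6, non-target CR is a non-PD state, so target PR with no new lesion gives PR.
4. Record B is slightly narrower than it looks. Section 9.3 counts a tumor marker still above normal as non-CR/non-PD. A patient whose non-target lesions are gone but whose marker remains raised can still meet the irPR condition. The affected patients are those with full non-target CR, including marker normalization where applicable.
5. Record C has nothing to which a lesion-level condition can apply. It can be read as not applicable (irPR) or as not met (irSD), and Appendix D does not say which. It meets the target-lesion definition of PR in Section 9.2.

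Size, as illustration only. Let p be the true response rate and g the share of all responders who present as record B. The rate lost if Section 3 prevails is p × g, and the expected number of patients rescored is n × p × g. The documents give no value for g. With n = 42 and p = 0.40 (the alternative in Section 12.1, which counts complete and partial RECIST responses together), each 10% in g costs 0.40 × 0.10 = 0.04, that is 4 percentage points, or 42 × 0.04 = 1.68 patients. At p = 0.20 it costs 0.20 × 0.10 = 0.02, or 42 × 0.02 = 0.84 patients. If g is zero, nothing is lost.

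**The case against.** A reader might infer something stronger: every patient must have measurable disease, irNN is confined to patients without target disease, so nobody can ever be irPR. The documents do not support that. The restricted irNN is an overall patient category, while the irPR condition speaks of the state of non-target lesions. Section 2.C spells the label out as non-CR/non-PD and brings in the RECIST 1.1 non-target definitions, and Section 9.3 attaches no requirement about target disease to that state. Appendix D read as a whole therefore offers a workable meaning, and a reading that empties the irPR category is not a reasonable one. This objection stands, and the first results column above should not be taken as what the plan prescribes.

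Three further objections deserve an answer.

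- Section 2.C would score records B and C as irPR, and nothing says that Section 3 prevails. This is correct, and it is why the under-count is a risk and not an established result. It does not remove the contradiction.
- The endpoint is descriptive, with no test or threshold. This also stands and limits the consequence.
- Appendix D is presented as taken from a published source, so the wording may be that source's shorthand. The source could not be checked. The protocol nevertheless adopts the text as its own rule, so the conflict has to be settled here.

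**Conclusion.** The contradiction between Appendix D Sections 2.C and 3 is real, and the Section 3 wording gives a wrong result for at least one ordinary record: a fall of at least 30% in TMTB with non-target CR and residual target disease. For patients with no non-target lesions the rule is unclear and not plainly wrong. The irRECIST response rate can be under-counted if assessors follow Section 3. It is not under-counted if they follow Section 2.C. The size cannot be derived from the documents, because it depends on the unknown share g, and the figures above are illustration only.

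A reader might also infer that the primary response test is affected, since Section 9.1 says that primary response is assessed by irRECIST. Sections 4.1.1 and 12.1 name RECIST for the primary endpoint, and on that basis the primary test and its power are untouched. The disagreement between those sections is a separate matter that needs its own reconciliation. If it were settled in favor of Section 9.1, the present point would carry more weight.

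**What to change.** In Appendix D, Section 3, keep the first and third irPR conditions and replace the middle one with: no irPD of non-target lesions (non-target lesions absent, resolved, or non-CR/non-PD). Reserve irNN for the overall assessment of patients without target disease. This agrees with Section 2.C and with Table 6. Because Table 6 also allows PR when non-target lesions are not all evaluated, the revision should say whether that holds for irPR too.

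The sponsor should compare the wording with the cited source and, if it departs from it, say so. The cost is a short text change to Appendix D, made before responses are tabulated, with any time-point assessments already coded checked against the new wording. No new scans or data are needed.
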